For patients who require dual chamber pacing, patients will be randomized to His bundle versus left bundle area pacing for active fixation. We will evaluate the acute and follow-up capture threshold of His bundle versus left bundle pacing.

Objectives

Primary Objective

To compare 3 month follow up complete ventricular capture thresholds of His bundle pacing versus left bundle area pacing lead placement. Complete loss of capture will be measured with a width of 1.0 ms and during unipolar or bipolar output, whichever value is lower.

Secondary Objectives

To compare changes in left ventricular performance and mechanical synchrony, selective or non selective-His Pacing, left bundle area pacing, in patients who require ventricular pacing at 3 months.

The endpoints collected will be:

1. Ejection Fraction
2. Stroke volume
3. Mechanical dyssynchrony, characterized by the time to peak systolic velocity of the Left Ventricle (LV) myocardial walls, elicited by tissue Doppler:
 - a. Anterior
 - b. Posterior
 - c. Anterior-Septal
 - d. Anterior-Lateral
 - e. Lateral
 - f. Inferior-lateral
4. QRS duration

Other secondary endpoints collected will be:

1. 6 month complete loss of capture threshold as defined in the primary endpoint.
2. 12 month complete loss of capture threshold as defined in the primary endpoint

Methods

Design

Single center, open label, randomized pilot study to evaluate the complete ventricular capture thresholds of His Bundle versus left bundle area pacing.

Secondary analysis will focus on echocardiographic hemodynamic parameters of HIS pacing, versus left bundle branch pacing.

Based on previous studies ([Vijayaraman, Naperkowski, et al., 2018](#)) and our experience with non-selective and left bundle area pacing, a difference of 0.5 V at 1.0 ms in capture threshold at 3 month follow-up between His and left bundle area pacing sites, is to be expected. With a standard deviation of 0.5 V, This would require an enrollment of 20 patients to obtain a power of 0.8 to demonstrate

statistical significance. Thus we anticipate enrollment of 26 patients to evaluate differences in capture threshold between the studied pacing sites, and an expected 20% patient drop out.

Enrollment

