Investigators providing care will be tasked with patient screening. This will be performed at both the inpatient and outpatient arenas, and can occur within any timeframe prior to the pacemaker implant. During the screening process, patients will be given consent forms to be reviewed collectively with an investigator.

Statistical Analysis

Continuous variables will be reported as mean +/- standard deviation. Categorical variables will be expressed as percentages. Paired comparisons will be made using a Student t-test if the data is normally distributed, and with the Wilcoxon signed-rank test for nonparametric data. Paired categorical data will be compared using the Wilcoxon test. P-value ≤ 0.05 was considered significant.

Randomization

Randomization will be in a 1:1 assignment. Twenty-six envelopes with random assignments to one of the two treatment arms will be created. As patients are enrolled, they will be assigned to an envelope. Each envelope number will be correlated with patient information, as well as date of procedure, and assigned ID number.

Randomization will occur after the patient demonstrates acceptable selective or non-selective HIS bundle pacing prior to active fixation.

If the patient is identified at the Beaumont Troy site, the above shall still continue to apply. The key personnel will bring the randomization card to the site on the day of the procedure.

Study Population

Inclusion Criteria

Prospective enrollment of patients:

1. Over 18 years old
2. Signed consent
3. Pacemaker indication according to 2018 ACC/ AHA HRS Guideline on the Evaluation and Management of Patients with Bradycardia and Cardiac Conduction Delay with one or more of the following
 - a. Symptomatic sinus node dysfunction.
 - b. Symptomatic Atrioventricular (AV) block or high degree AV block.
 - c. Tachy-Brady syndrome

Exclusion Criteria

Patients with any condition of the following will be excluded:

1. Previously implanted cardiac pacing devices except transvenous temporary pacemaker.
2. Patients who are eligible for appropriate cardiac resynchronization therapy(CRT) or implantable cardiovert defibrillator (ICD) implantation
3. Patients with prior septal myectomy
4. Patients with prior surgical or transcatheter aortic valve replacement
5. Anatomy precluding implant evaluated during the screening or identified during the procedure.

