A standard of care echo done within 3 months of the procedure will be used as the baseline echo. Data acquired from the echo will be and assessed by a single, non-blinded Cardiac Echocardiographer. Tissue doppler if not performed during the echo, post processing will be utilized if possible.

To evaluate the hemodynamic properties of the pacing site, echocardiography will be utilized.

Hemodynamic assessment will be obtained by collecting stroke volume at each site, utilizing the velocity time integral. The VTI will be obtained in the apical long axis view.

Left ventricular ejection fraction will also be assessed at each pacing site utilizing the biplane method of disks.

Tissue Doppler imaging will be used to assess longitudinal LV dyssynchrony. Myocardial velocity curves are to be obtained from the apical 2 and 3 chamber views. These views are selected to assess the anterior, inferior, lateral anterior-septal, inferior-septal, and inferior lateral left ventricular walls. The peak sustained myocardial systolic velocity (during the ejection phase) for each of the 4-LV segments is to be identified. The time to peak systolic velocity will be measured with reference to the onset of QRS complex.

The following data will be collected:

1. Left ventricular Ejection Fraction
2. Stroke volume (by VTI)
3. The peak sustained myocardial systolic velocity (during the ejection phase) for each of the 4-LV segments is to be identified:
 - a. Anterior
 - b. Anterior-Septal
 - c. Inferior-Septal
 - d. Inferior
 - e. Inferior-lateral
 - f. Lateral

Electrocardiographic evaluation

During the procedure, a 12-lead electrocardiogram will be available, and recorded while atrio-ventricular paced. The following will be collected:

1. The stimulation-to-QRS
2. QRS duration
3. QRS morphology
4. Pacing stimulus to left ventricular activation time (LVAT) in unipolar lateral precordial leads V4-V6

The following will be collected after active fixation, during the most narrow QRS morphology obtained:

1. The stimulation-to-QRS
2. QRS duration
3. QRS morphology
4. Pacing stimulus to left ventricular activation time (LVAT) in unipolar lateral precordial leads V4-V6

Procedural Data

Data collected will be:

1. Fluoroscopic time
2. Amount of contrast administered
3. Procedural time

Device Evaluation

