Intra procedural data will be collected. After active fixation of the lead, the capture threshold will be collected. A pulse width of 1.0 ms will be used in all patients. Selective Left bundle branch (LBB) pacing (S-LBBP) is defined as only capturing the LBB without myocardial capture, with a discrete isoelectric component between the pacing stimulus and the onset of QRS complex in the electrocardiogram (ECG) and electrogram(EGM)s recorded by the EP system and the programmer. Nonselective LBB pacing (NS-LBBP) captured both the LBB and the local myocardium around the lead without the discrete isoelectric component. Selective HIS bundle (HB) pacing (S-HBP) is defined as only capturing the HB without myocardial capture, with a discrete isoelectric component between the pacing stimulus and the onset of QRS complex in the electrocardiogram (ECG) and electrogram (EGM)s recorded by the EP system and the programmer. Nonselective HB pacing (NS-HBP) captured both the HB and the local myocardium around the lead without the discrete isoelectric component. We will measure the pacing stimulus to left ventricular activation time (LVAT) in unipolar lateral precordial leads V4-V6 defined as the stimulus to the peak of the R wave and the paced QRS morphology.

Data Collected:

Unipolar

1. Selective Capture
2. Non-selective
3. Complete loss of capture
4. Impedance values at the site of active fixation will be collected
5. Sensed R wave amplitudes

Bipolar

1. Selective Capture
2. Non-selective
3. Complete loss of capture
4. Impedance values at the site of active fixation will be collected
5. Sensed R wave amplitudes

Post-Procedure Data

The following day, patient will receive a PA and lateral chest X-Ray.

A 12-lead electrocardiogram will be obtained while the patient is set to a parameter that ensures selective His ventricular pacing or the narrowest QRS achievable with left bundle area pacing, depending on the randomization group.

The following will be collected during pacing which yields the most narrow QRS:

1. The stimulation-to-QRS
2. QRS duration
3. QRS morphology
4. Pacing stimulus to left ventricular activation time (LVAT) in unipolar lateral precordial leads V4-V6

The device will be interrogated to obtain the following:

Unipolar

1. Selective Capture
2. Non-selective
3. Complete loss of capture
4. Impedance values at the site of active fixation will be collected
5. Sensed R wave amplitudes

Bipolar

1. Selective Capture
2. Non-selective

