3. Complete loss of capture
4. Impedance values at the site of active fixation will be collected
5. Sensed R wave amplitudes

At 3 months the patient will have a limited echocardiogram while the patient is set to parameter that ensures AV synchronous, selective HIS pacing or the narrowest QRS achievable with left bundle area pacing, depending on the randomization group. The echo will be performed by sonographer and included in the budget. The following echo data will be collected at 3 months:

1. Left ventricular Ejection Fraction
2. Stroke volume (by VTI)
3. The peak sustained myocardial systolic velocity (during the ejection phase) for each of the 4-LV segments is to be identified:
 - a. Anterior
 - b. Anterior-Septal
 - c. Inferior-septal
 - d. Inferior
 - e. Inferior-Lateral
 - f. Lateral

4. The distance from the septal leaflet of the tricuspid valve to the entry point in the RV septum was measured from a standard 4-chamber view.
5. The length on penetration of the RV His or left bundle area lead into the myocardium
6. The degree of tricuspid regurgitation (TR)

Potential Risks

Adverse outcomes will be collected, and compared between the His bundle, and left bundle area pacing cohorts. These will include:

1. Lead pacing exit block
2. Threshold increase (defined as an increase in chronic pacing threshold >1 V at 1.0 ms)
3. Lead dislodgment
4. Need for lead revision.

Complications associated with device implantation will be recorded. Potential risks of any pacemaker implant, which may require additional reparative operations include

1. Excessive bleeding and pocket hematoma, requiring evacuation or transfusion)
2. Infection
3. Pneumothorax
4. Vascular injury
5. Cardiac perforation and tamponade
6. Lead dislodgement requiring revision
7. Radiation exposure
8. Pain at the incision site

Potential risks to the patient beyond those attributable to routine pacemaker implant are:

1. Additional contrast exposure
2. A theoretical interventricular septal puncture into the left ventricle with the active fixation of the screw if using the left bundle area location.

Interventricular septal puncture has been reported at a rate of 3 % in prior literature, which was corrected without any long term complication ([Vijayaraman P & Mascarenhas V, 2019](#)

)

Potential Benefits

Potential benefits are derived from recent studies ([Vijayaraman, Naperkowski, et al., 2018](#)), which include:

1. Decreased rate of hospitalization for heart failure
2. Increased LVEF

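### Mechanical dyssynchrony is defined wall by wall with no within-patient spread between walls, so the planned measure may miss a true difference in synchrony or show one where there is none.

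*Combined protocol and SAP*

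**What the plan says.** The objective under Secondary Objectives is "To compare changes in left ventricular performance and mechanical synchrony" at 3 months. Endpoint 3 is "Mechanical dyssynchrony, characterized by the time to peak systolic velocity of the Left Ventricle (LV) myocardial walls, elicited by tissue Doppler", followed by six named walls.

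The Echocardiographic Evaluation Protocol states the purpose ("Tissue Doppler imaging will be used to assess longitudinal LV dyssynchrony") and the reference point ("The time to peak systolic velocity will be measured with reference to the onset of QRS complex"). The data list under the same heading records something else: "The peak sustained myocardial systolic velocity (during the ejection phase) for each of the 4-LV segments is to be identified". Six walls follow. The 3-month echo list under Follow-up repeats that item.

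Statistical Analysis says "Continuous variables will be reported as mean +/- standard deviation" and names only paired tests. No section derives an SD across walls, a maximum wall-to-wall delay or any other per-patient index, and none says how six walls lead to a conclusion about synchrony.

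**The concern.** Synchrony is a relation between walls in the same heart. Six wall times, each averaged over the patients in an arm, do not measure that relation. Two errors are possible. If different walls are late in different patients, the lateness spreads thinly over all six means. If all walls are late by the same amount, every mean moves although the walls still contract together.

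What is at stake is whether the trial can answer its synchrony objective. A spread chosen after the data are in would be weak evidence, because the study is open label and the echocardiographer who assesses the baseline echo is not blinded.

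**Working it through.** **Inputs.** The documents give no wall times, effect size or power for this endpoint, so there is no planned figure to reproduce. The 20 evaluable and 26 enrolled patients relate to capture threshold. They are used here only to set arm sizes: 20/2 = 10 and 26/2 = 13. All times below are assumptions.

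**1. Hand example.** In arm A (six patients), a different wall peaks at 210 ms in each patient and the other five peak at 150 ms. In arm B, every wall peaks at 160 ms.
- Mean of each wall in arm A: (5 × 150 + 210)/6 = 160 ms, equal to arm B.
- Within-patient SD in arm A: √[(5 × 10² + 50²)/5] = √600 = 24.5 ms, against 0 in arm B.
- Maximum delay: 210 − 150 = 60 ms, against 0.

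The exact tie depends on placing arm B at 160 ms. At 150 ms, every wall would differ by 10 ms, which would look like a small uniform delay and not like dyssynchrony.

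**2. Why a spread is unaffected by a common delay.** Write the time for wall j in patient i as c_i + w_ij, where c_i is common to all walls. The SD or range over j does not contain c_i, but each wall mean does.

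**3. Simulation.** There were 5,000 trials per scenario, with six walls and two-sample t-tests at two-sided 0.05. Assumed: mean 200 ms, between-patient SD 20 ms, wall noise SD 10 ms, shift 50 ms, 10 per arm.

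| Scenario | Each wall test rejects | At least one of six | Spread test rejects |
|---|---|---|---|
| No difference | about 5% | 14% | about 5% |
| One early and one late wall, varying between patients | about 5% | 24% | about 100% |
| Same early and same late wall in every patient | 99.7% for those two, about 5% for the rest | about 100% | about 100% |
| All walls delayed equally | over 99% | about 100% | about 5% |

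In the second row the mean within-patient SD was 9.5 against 32.9 ms, and the mean range 25 against 100 ms. The second-row pattern also held with shifts of 30 and 80 ms at 10 per arm, and all four rows held at 13 per arm with 50 ms.

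**4. Check by formula.**
- The SD of one wall between patients is √(20² + 10²) = 22.4 ms. The standard error of a difference with 10 per arm is 22.4 × √(2/10) = 10.0 ms, so a consistent 50 ms shift is 5 standard errors.
- With varying walls, the expected shift of each wall is (1/6)(50) + (1/6)(−50) = 0.
- The within-patient SD is about √(10² + 2 × 50²/5) = √1100 = 33.2 ms, close to the simulated 32.9.

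**5. The lists side by side.** Secondary Objectives names anterior, posterior, anterior-septal, anterior-lateral, lateral and inferior-lateral walls. The two echo data lists name anterior, anterior-septal, inferior-septal, inferior, inferior-lateral and lateral. Four names agree. Posterior and anterior-lateral appear only in the first list, and inferior and inferior-septal only in the others. Both data lists refer to four segments above six walls.

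**The case against.** **A consistent pattern would be seen.** Each arm has one designated pacing site, so the same walls may well be affected in most patients. Wall means then detect it, as the third row shows. This stands. A reader might infer that the endpoint is blind to dyssynchrony; it is not. The documents give no data to say which pattern applies.

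**The plan reports SDs as well as means.** In the hand example each wall would read 160 ± 24.5 ms in arm A and 160 ± 0 in arm B, so the report would not look identical. This also stands. But ordinary variation between patients blurs the signal: under the simulation's assumptions the per-wall SD would be 22.4 ms against √(22.4² + 50²/3) = 36.5 ms. No test of that SD is planned.

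**No wrong analysis is stated.** The plan is silent on derivation, and six wall-by-wall comparisons are an inference from the list of walls and the general statistics paragraph. That is fair. The defect is the missing definition.

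**Capture type.** A reader might infer that wall times must shift with capture type, because Device Evaluation defines selective capture as "without myocardial capture, with a discrete isoelectric component between the pacing stimulus and the onset of QRS complex". The documents do not support this. That interval lies before QRS onset, and the times are measured from QRS onset, so it is outside them. A common shift would require wall timing to stay fixed to the stimulus while QRS onset moves, which no section says. The 3-month echo is also specified under selective pacing in the His arm, which limits mixing within that arm though not a difference between arms. The stimulus-to-QRS interval is collected at 3 months, so such a shift could be examined.

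**The velocity wording is minor.** Partly so: the Echocardiographic Evaluation Protocol text does say that the time will be measured. The lists that define what is recorded still do not name it.

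**Conclusion.** The concern holds as a gap in definition. The plan names synchrony as the objective, lists wall times as the measure, and specifies nothing that turns those times into a measure of synchrony. Wall-by-wall means may miss a true difference (about 5% rejection against about 100% for a spread) or show a difference without dyssynchrony (over 99% against about 5%). These figures rest on assumed wall times, and the miss also requires that the affected walls vary between patients.

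Two stronger readings are not supported: that the endpoint can never show a difference, and that capture type necessarily shifts the times. The latter is a possible cause of a common delay, and only an assumption.

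This is a secondary endpoint of a pilot study. The primary comparison of capture thresholds is not affected, but the correction is cheap and should be made before any analysis.

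**What to change.** 1. Reconcile the wall lists in Secondary Objectives, the Echocardiographic Evaluation Protocol and Follow-up, including the count of four segments above six walls.
2. In both echo data lists, add time to peak systolic velocity from QRS onset as a recorded item for each wall.
3. Prespecify one number per patient, for example the SD of time to peak across the reconciled walls. Make maximum wall-to-wall delay supportive, and set a minimum number of readable walls.
4. Compare that number between arms at 3 months with an unpaired test (two-sample t or Wilcoxon rank-sum), since only paired tests are now named. Report change from baseline as supportive where baseline tissue Doppler exists; the plan makes its post-processing conditional on feasibility.
5. Keep individual wall times as descriptive, because a spread does not show which wall is late.

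The cost is endpoint wording and one derived variable from times that the plan already intends to measure, with no new images. The small downside is that patients with too few readable walls drop out of this secondary analysis, so their number should be reported by arm.

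### Twenty patients in two randomised arms give power of about 0.56, not 0.8, for a 0.5 V difference with SD 0.5 V; 34 evaluable patients would be needed

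*Combined protocol and SAP*

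**What the plan says.** The introductory statement of the combined protocol and SAP says that "patients will be randomized to His bundle versus left bundle area pacing for active fixation". The Primary Objective is "To compare 3 month follow up complete ventricular capture thresholds of His bundle pacing versus left bundle area pacing lead placement".

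Under Methods, Design, the plan expects "a difference of 0.5 V at 1.0 ms in capture threshold at 3 month follow-up between His and left bundle area pacing sites". It continues: "With a standard deviation of 0.5 V, This would require an enrollment of 20 patients to obtain a power of 0.8 to demonstrate" statistical significance. The next sentence reads "Thus we anticipate enrollment of 26 patients to evaluate differences in capture threshold between the studied pacing sites", with an allowance for 20% drop-out.

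The Randomization section specifies 1:1 allocation and says "Twenty-six envelopes with random assignments to one of the two treatment arms will be created". The Statistical Analysis section sets significance at P ≤ 0.05 without saying whether tests are one- or two-sided. The tests it names (Student t-test, Wilcoxon signed-rank) are described for paired comparisons.

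**The concern.** The plan gives every input needed to check its power statement except sidedness, and the inputs do not lead to 20 patients. For two independent groups and an effect of one standard deviation, a total of 20 is well short of what 80% power requires.

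Power is the only justification offered for the sample size, and it concerns the primary endpoint. If the figure is wrong, the trial is much more likely to miss the difference it expects than the protocol says. A non-significant result would also carry a stated power of 0.8 that the design does not have.

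**Working it through.** **Inputs**

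| Quantity | Value | Source |
|---|---|---|
| Difference, δ | 0.5 V | Methods, Design |
| Standard deviation, σ | 0.5 V | Methods, Design |
| Stated power and N | 0.8 with 20 patients | Methods, Design |
| Enrolment and drop-out | 26; 20% | Methods, Design |
| Allocation | 1:1, 26 envelopes | Randomization |
| Significance level | 0.05 | Statistical Analysis |
| Sidedness | not stated; two-sided assumed, one-sided also tried | – |

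The standardised effect is d = δ/σ = 0.5/0.5 = 1.0. One ventricular lead site per patient means two independent samples; 20 evaluable patients at 1:1 is 10 per arm.

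**Trying to reproduce the plan's figure**

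- *Drop-out step.* 20/(1 − 0.2) = 25, and 26 × 0.8 = 20.8. The step from 20 to 26 is sound.
- *Required number, normal approximation.* n per arm = 2(1.960 + 0.842)²/d² = 15.7, so 16 per arm, 32 in total. Not 20.
- *Required number, t-test.* The exact (noncentral t) solution is 16.7, so 17 per arm, 34 in total. Not 20.
- *20 read as per arm.* Power would be 0.87, but that means 40 patients, against 26 envelopes.
- *Paired test.* If 0.5 V were the SD of within-patient differences, n = 9.94, so 10 pairs (power 0.803). This comes to 20 only if 10 pairs are counted as 20 patients.

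The paired route is the only one found that leads to 20. That it is the origin is inference, because the plan gives no formula. It cannot apply here in any case: no patient supplies a 3-month threshold at both sites.

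**Power the design has**

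For n per arm, the noncentrality parameter is d√(n/2) with 2n − 2 degrees of freedom. At n = 10 this is √5 = 2.236 on 18 df, against a two-sided critical value of 2.101.

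| n per arm | Total | Power, two-sided 0.05 | Power, one-sided 0.05 |
|---|---|---|---|
| 10 | 20 | 0.562 | 0.694 |
| 13 | 26 | 0.687 | 0.797 |
| 16 | 32 | 0.781 | 0.868 |
| 17 | 34 | 0.807 | 0.886 |

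The normal approximation gives 0.609 (two-sided) and 0.723 (one-sided) at 10 per arm. An 11/9 split gives 0.558 (two-sided t). For 0.8 with a one-sided test, the t-test needs 13.1 per arm, so 14 per arm or 28 in total; the normal approximation gives 26.

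**What 20 evaluable patients can show (two-sided)**

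- Difference detectable with 80% power: 0.66 V (0.57 V at 13 per arm).
- SD at which 0.5 V would be detectable with 80% power: 0.38 V, not 0.5 V.
- Expected 95% CI half-width: 2.101 × 0.5 × √(2/10) = 0.47 V, nearly the whole assumed difference.
- Chance of missing a true 0.5 V difference: 1 − 0.56 = 0.44.

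**Enrolment needed to keep the 0.8 statement (two-sided)**

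34/0.8 = 42.5, so 43 enrolled, or 44 for equal arms.

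**The case against.** The strongest point is sidedness. The plan never says the test is two-sided, so 0.56 and 34 rest on an assumption. Across one- and two-sided tests, by t-test or normal approximation, power at 20 patients runs from 0.56 to 0.72, the required total from 34 down to 26, and the chance of missing a true difference from 44% down to 28%. One-sided, with all 26 patients evaluable, power is 0.797, essentially the stated value. This range stands and should accompany the headline figure. It does not rescue the sentence: the plan claims 0.8 at 20 patients and assigns the other six to drop-out, and no entry in the range reaches 0.8 at 20.

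Second, this is a pilot, and a pilot need not be powered. That lowers the consequences. But the protocol makes an explicit power statement, and it has to be right on its own inputs.

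Third, the protocol plans no equivalence or non-inferiority claim, so how a null result would be read is a matter of judgement. That is fair. The error in the power figure does not depend on it.

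Fourth, correcting the Design paragraph alone would leave it citing a two-sample test that the Statistical Analysis section does not name. This stands as a reason for a companion edit, not as a defence of the figure.

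**Conclusion.** The concern holds. On the plan's own inputs, 20 evaluable patients in two arms give power 0.56 with a two-sided 0.05 two-sample t-test, and 26 give 0.69; 34 evaluable are needed for 0.8. This assumes equal arms, a common SD of 0.5 V, approximate normality and two-sided testing. Only the last materially affects the size of the shortfall among the readings tried, and under the one-sided alternative power at 20 is still only 0.69 to 0.72. The stated power is wrong as written and must be corrected.

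**What to change.** Replace the sample-size sentence in Methods, Design with wording such as:

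> With 20 evaluable patients (10 per arm), SD 0.5 V and a two-sided two-sample t-test at 0.05, power to detect 0.5 V is about 56% (69% if all 26 are evaluable). The difference detectable with 80% power is about 0.66 V. The expected 95% CI half-width is about 0.47 V.

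Add that, as this is a pilot, the primary result will be reported as an estimated difference with its 95% CI, and that a non-significant result is not evidence of equal thresholds. As a companion edit, name the two-sided two-sample test for the between-arm comparison in Statistical Analysis so that the two sections agree.

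The cost is protocol wording and a less favourable stated power; no extra patients are needed. If the sponsor prefers to keep 0.8 on these inputs, the alternative is to enrol about 43 patients (44 for equal arms) in place of 26 and to prepare the extra envelopes.

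### The plan commits to no between-arm difference or confidence interval, so a non-significant primary result could be read as no difference without excluding the planned 0.5 V

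*Combined protocol and SAP*

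**What the plan says.** The Design section describes a "Single center, open label, randomized pilot study to evaluate the complete ventricular capture thresholds" of the two pacing sites. The Primary Objective is a comparison of the randomized arms at 3 months. The sample size rests on "a difference of 0.5 V at 1.0 ms in capture threshold at 3 month follow-up between His and left bundle area pacing sites", and continues: "With a standard deviation of 0.5 V". For the numbers it states "This would require an enrollment of 20 patients to obtain a power of 0.8 to demonstrate" significance, and then "Thus we anticipate enrollment of 26 patients to evaluate differences in capture threshold between the studied pacing sites", allowing for 20% dropout. Allocation is 1:1.

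The Statistical Analysis section is a short paragraph. For summaries: "Continuous variables will be reported as mean +/- standard deviation". For testing: "Paired comparisons will be made using a Student t-test if the data is normally distributed", with a signed-rank test otherwise. For the decision: "P-value ≤ 0.05 was considered significant". It does not say whether the test is one- or two-sided, and it does not confine the rule to the primary endpoint.

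No section mentions a confidence interval, an estimated difference between arms, or how a P-value above 0.05 is to be interpreted. None of the secondary endpoints is labelled exploratory.

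**The concern.** The trial exists to learn how far the 3-month thresholds differ between two pacing sites, yet that difference and its precision are not planned outputs. With 20 to 26 patients, a P-value above 0.05 is consistent both with no difference and with a difference of the planned size, and the P-value alone does not separate them. A pilot is used mainly to inform what comes next, so a report that stops at means, SDs and a verdict could lead a later team to drop a difference that the data never excluded.

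The same rule applied to every secondary endpoint carries the opposite risk. One isolated P-value at or below 0.05 among several could be reported as a finding.

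**Working it through.** **Inputs.** Design section: difference 0.5 V, SD 0.5 V, power 0.8, 20 evaluable, 26 enrolled, 20% dropout. Randomization section: 1:1, so 10 per arm evaluable or 13 per arm if nobody drops out. Statistical Analysis section: 5% level. Two-sided testing is my assumption.

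**The plan's own figure.** For two independent arms, n per arm = 2 × (1.96 + 0.84)² × (0.5/0.5)² = 15.7, so 16 per arm, 32 in all (17 per arm, 34 in all, with the t distribution). One-sided gives 26 (28 with t). None of these is 20. The only match found is a paired t-test with an SD of differences of 0.5 V, which needs 10 pairs, doubled to 20; that does not fit parallel arms. The dropout step is consistent: 20/0.8 = 25, and 26 makes the arms even. At 10 per arm the two-sided power for 0.5 V is 0.56 by the t-test.

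**Width of the missing interval.** Half-width = t(0.975, 2n − 2) × SD × √(2/n).
- 10 per arm: 2.101 × 0.5 × √(2/10) = 2.101 × 0.2236 = 0.470 V.
- 13 per arm: 2.064 × 0.5 × √(2/13) = 2.064 × 0.1961 = 0.405 V.

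**What a non-significant result could exclude**, if the observed SD equals 0.5 V. The result is non-significant when the observed difference lies within the half-width of zero. The interval excludes +0.5 V only when the observed difference is below 0.5 minus the half-width.
- 10 per arm: 0.5 − 0.470 = 0.03 V.
- 13 per arm: 0.5 − 0.405 = 0.095 V.

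The plan does not say which site is expected to have the higher threshold. To exclude 0.5 V in both directions, the observed difference must lie within ±0.03 V or ±0.095 V respectively.

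**How often this would arise.** Simulation of 400,000 normal trials per row, SD 0.5 V:

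| Per arm | True difference | Non-significant | Of those, interval includes +0.5 V | Includes +0.5 or −0.5 V |
|---|---|---|---|---|
| 10 | 0 | 95% | 43% | 81% |
| 10 | 0.25 V | 82% | 78% | 88% |
| 10 | 0.5 V | 44% | 94% | 96% |
| 13 | 0 | 95% | 30% | 60% |
| 13 | 0.25 V | 77% | 70% | 75% |
| 13 | 0.5 V | 31% | 92% | 92% |

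The rows for 0 and 0.25 V carry the information. In the 0.5 V rows, high inclusion is close to automatic, because a 95% interval is built to cover the true value.

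**Secondary endpoints.** The Secondary Objectives list six: ejection fraction, stroke volume, dyssynchrony, QRS duration, and the 6- and 12-month thresholds. Counting each of the six walls under dyssynchrony separately gives 3 + 6 + 2 = 11. If no true effects exist and the tests are independent, the chance of at least one P ≤ 0.05 is 1 − 0.95⁶ = 26% for six and 1 − 0.95¹¹ = 43% for eleven.

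**The case against.** Four points can be made for the plan.

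- **The misreading is not in the text.** A reader might infer that the plan will declare no difference, or equivalence, whenever P exceeds 0.05. It does not say so: there is no interpretation rule, and no equivalence or non-inferiority claim. This stands, and is why the point is only that the result could be read that way.
- **Little is lost if mean, SD and n are reported by arm**, because a reader can then work out the interval. This stands in part. The section does not say summaries will be by arm, the calculation is not available from a rank-test result, and the plan still would not commit to interpreting the precision.
- **The 44% non-significant rate is a sample-size problem.** A reader might blame it on the reporting plan. It is one minus the power at 10 per arm, and adding an interval leaves it unchanged. This stands, and the rate is not counted here. The reporting gap would remain with more patients: at 17 per arm, which gives 80% power, the half-width is still 0.35 V.
- **The secondary endpoints already rank below one primary.** A reader might infer a 43% chance of a false-positive claim. That needs each wall to be tested separately, which the document does not say, and independence, which is unlikely for wall timings from one echocardiogram or thresholds from one lead. This stands: 43% is the upper end of the range and 26% is the figure for the listed endpoints, both lower under positive correlation. What remains is that the 0.05 rule is not restricted.

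**Conclusion.** The point holds as a gap in what the plan commits to report. At the planned SD, the interval for the primary difference is nearly as wide on each side as the effect the trial was sized on: ±0.47 V with 20 evaluable patients and ±0.40 V with all 26. Most non-significant results would leave +0.5 V open if the true difference is 0.25 V (78% and 70%); a minority would if it is zero (43% and 30%). The statement that most non-significant results stay compatible with 0.5 V therefore depends on the truth assumed, unless both directions are counted.

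These figures assume an SD of 0.5 V, normal data, equal arms and two-sided 5% testing. Two neighbouring defects, the paired tests named for independent arms and the shortfall in power, are separate. Correcting either alone would still leave no planned estimate or interval. The data collected remain valid, so this should be changed but does not threaten the trial.

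**What to change.** In the Statistical Analysis section:

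1. Define the primary result as the His minus left bundle difference in 3-month capture threshold, in volts, with a two-sided 95% confidence interval and the P-value beside it.
2. Fix in advance a method for independent arms, for example Welch's t. If a non-normal route is kept, use the Hodges-Lehmann estimate with its interval and state beforehand what triggers it.
3. State that the interval will be read against 0.5 V, and that P > 0.05 will not be reported as no difference if the interval includes 0.5 V in either direction. Excluding 0.5 V rules out a difference of the planned size; the plan sets no equivalence margin, so it should not be called equivalence.
4. Report secondary endpoints as between-arm differences with 95% intervals, labelled exploratory, and reserve the 0.05 rule for the primary.

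The cost is a few sentences and slightly longer tables, with no extra patients, visits or measurements. The one thing given up is calling a secondary result significant.
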